Azathioprine is first converted to 6-mercaptopurine in the liver. In red blood cells, hypoxanthine guanine phosphoribosyltransferase (HPRT) converts 6-mercaptopurine to 6-thioninosine-5' monophosphate, which is then converted to either 6-thioguanine nucleotides (6-TG) or 6-methyl-mercaptopurine ribonucleotides (6-MMP). 6-TG is the metabolite that is associated with immunosuppression, and thus may help decrease disease activity and lead to or maintain remission in IBD (Belaiche et. al, 2001, p. 72). It has a long half-life in red blood cells and other tissues. Thus, prolonged treatment is needed for it to accumulate to steady-state levels (p. 72). 6-TG is also cytotoxic and associated with suppression of bone marrow at levels greater than 400 pmol/8x10⁸ RBC (MacDermott, 2016). However, levels between 230 and 400 pmol/8x10⁸ RBC seem to be optimal for treating IBD and achieving remission. The other end metabolite of azathioprine/6-mercaptopurine, 6-MMP, is associated with hepatotoxicity at levels greater than 5700 pmol/8x10⁸ RBC (MacDermott, 2016). If thiopurine methyltransferase (TPMT) is deficient, bone marrow toxicity can occur due to elevated levels of 6-TG nucleotides. Thus, it is important to monitor the metabolism of azathioprine and 6-mercaptopurine through the levels of 6-TG and 6-MMP.

Methods

Research design: The study will be a prospective study in a cross over design, with each patient acting as a control for him/herself. Subjects will be patients contacted from a Rush University Medical Center database that are currently prescribed azathioprine and/or 6-mercaptopurine. They will be asked to take their medication at a determined time each day (morning or evening), complete questionnaires, and come in to get labs drawn. Data obtained will be analyzed according to statistical methods listed below in order to determine significance of association.

Power and Sample Size: There have been no prior studies testing the role of chronotherapy and IBD, therefore no knowledge exists on the anticipated effect. We aim for a prospective study to offer enrollment to all subjects who meet the study qualifications. For a mean difference of 5% and standard deviation of 20, we calculated that we will need to enroll 128 subjects to provide a power of 80% for a significance level of $\alpha=0.05$.

Inclusion Criteria: Patients with IBD who have taken, or are currently taking, azathioprine or 6-mercaptopurine.

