Description of Procedures: After signing the informed consent form, subjects will be asked to answer the Inflammatory Bowel Disease Questionnaire (IBDQ), the Munich Chronotype Questionnaire (MCTQ), the Owl and Lark Questionnaire, the Harvey Bradshaw questionnaire, the RU SATED questionnaire, and a demographics survey. All six of these questionnaires are included with this IRB. Next, patients will be assigned a time (morning or evening) to self-administer their prescribed medication for 10 weeks. Patients who currently take their medication in the morning will be asked to switch to an evening delivery and patients who currently take their medication at night will be asked to switch to a morning delivery. The group assigned to morning delivery time will be told to take their medication between 6am and 11am. The group assigned to evening delivery time will be told to take their medication between 6pm and 11pm. Lastly, patients will be asked to give a blood sample to test for complete blood count (CBC), comprehensive metabolic panel (CMP), C-reactive protein (CRP), methylmercaptopurine (6-MMP), and thioguanine nucleotides (6-TG). Plasma and serum isolated from the blood sample will be temporarily stored to measure inflammatory cytokines after every 20 subjects complete the study.

Within a 6-10 week window, as part of their clinical care, subjects will come in to assess their clinical status while undergoing biochemical monitoring every 2-4 weeks. Data from their endoscopic examination, if done, will also be collected.

After 10 weeks, the subjects will be asked to complete the IBDQ and Harvey Bradshaw questionnaire. In addition, a blood sample will be obtained to measure the same metabolite levels and other biochemical indications of disease as stated above. Again, plasma and serum will be isolated from the blood sample and stored.

Study Design Flow:

Subjects on azathioprine or 6-mercaptopurine from Rush database that satisfy inclusion criteria recruited for study and consented

Questionnaires administered: IBDQ, Owl and Lark, Harvey Bradshaw, MCTQ, SATED,
demographics
Blood draw

Morning or evening group for delivery based on previous time of medication administration

After 10 weeks: Re-administer Harvey Bradshaw and IBDQ surveys and a second blood draw

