All power estimates were computed using R package pwr, and we assume a Type I error rate of 0.05 and a 2-sided test for all analyses. Power estimates were derived from the data from prior unpublished studies. The primary endpoint of this study will be metabolites of 6-mercaptopurine. For Aim 1, previous studies have found that circadian enzymes can alter metabolites about 12% by different circadian controlled genes. With 128 UC subjects and effect size of 0.1 this will give us a 98% power to detect a difference in serum metabolites with a paired Wilcox Signed Rank test at alpha=0.05 level, and 84% power if gender is used as an independent variable. These conservative estimates provide a good estimate of the power to detect differences in metabolites chronotherapy in IBD patients. We anticipate we will have nonparametric data and will use the Wilcoxon match-pair test for analysis for inflammatory cytokines. This will be a nonrandomized trial that will not control for order effects, but other factors that are recorded such as cigarette smoking will be used as a covariate in multivariate analysis with analysis of variance (ANOVA) and linear regression as indicated. For Aim 2, a validated chronotype questionnaire (Munich Chronotype Questionnaire) will be compared optimal 6-mercaptopurine. Corrected midpoint of sleep will then be compared to 6-MP metabolites to see if chronotype impacts metabolite profiles. Data will be presented as median \pm range for variables that can be considered nonparametric. All analyses will use R (v.3.2.5) and SPSS (SPSS Inc., Chicago, IL).

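### Doses taken and prescribed dose are not described as recorded, so a change in metabolite levels cannot be attributed to enzyme timing; the 6-MMP:6-TG ratio would help with part of this

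*Combined protocol and SAP*

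**What the plan says.** Description of Procedures states that "patients will be assigned a time (morning or evening) to self-administer their prescribed medication for 10 weeks". Morning takers move to evening and evening takers to morning, so every patient leaves an established dosing time. 6-TG and 6-MMP are measured at the start and again after 10 weeks. Study and Data Analysis makes 6-mercaptopurine metabolites the primary endpoint, without defining a level, ratio or category, and says that the trial is non-randomised and does not control for order.

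The list under Data Collection gives the name of the prescribed drug but neither its dose nor the amount taken. No diary, pill count, refill check or missed-dose question is described. Of the six baseline questionnaires, only the IBDQ and Harvey Bradshaw are repeated at week 10.

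Three effect figures appear:
- Power and Sample Size: "For a mean difference of 5% and standard deviation of 20", the authors calculate that "we will need to enroll 128 subjects to provide a power of 80" per cent.
- Study and Data Analysis, as background to Aim 1: "previous studies have found that circadian enzymes can alter metabolites about 12% by different circadian controlled genes".
- The same section, for power: "With 128 UC subjects and effect size of 0.1 this will give us a 98% power to detect a difference in serum metabolites".

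On mechanism, section 3 of the Background takes azathioprine to 6-mercaptopurine, then through HPRT to an intermediate, "which is then converted to either 6-thioguanine nucleotides (6-TG) or 6-methyl-mercaptopurine ribonucleotides (6-MMP"). Study and Data Analysis rests the study on circadian oscillation of the drug-metabolising enzymes in general.

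**The concern.** A metabolite level reflects how much drug was swallowed as well as how it was metabolised. Leaving a habitual time may cost some doses; being enrolled and instructed may add some. With no group that stays on its usual time, either change enters the paired difference directly.

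A rise or fall in levels could therefore be read as circadian metabolism when it is pill-taking, and a real metabolic effect could be hidden by an opposite change in adherence. A change in prescribed dose would act the same way. The study does not alter dose, but the Background says that laboratory monitoring of these drugs guides dose changes, and patients are monitored every 2 to 4 weeks.

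**Working it through.** **Inputs from the documents:** N = 128, difference 5%, SD 20 (Power and Sample Size); two-sided 0.05 and the 12% (Study and Data Analysis); 10 weeks, both metabolites at both draws (Description of Procedures); the order of the metabolic steps (Background, section 3).

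**Assumptions, not in the documents:** levels are proportional to doses taken at steady state; one dose a day, so 70 doses; baseline adherence 70% to 100%; the SDs and half-lives named below.

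**1. The plan's sample size.** Standardised difference = 5/20 = 0.25. Normal approximation: n = [20 × (1.960 + 0.842)/5]² = 125.6. The paired t-test gives n = 128 with power 80.15%. The figure reproduces as a within-patient calculation, so 5% is the difference behind N = 128. The effect size of 0.1, read as a paired standardised effect, gives 20% power rather than 98%, so I do not use it as a benchmark.

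**2. Adherence converted to level.** Relative change = new adherence / old adherence − 1.
- 0.95/0.85 − 1 = +11.8%; 0.90/0.80 − 1 = +12.5%; 0.85/0.95 − 1 = −10.5%.
- Doses of 70 needed = 70 × baseline adherence × relative change.
- For 12%: 70 × 0.70 × 0.12 = 5.9, up to 70 × 1.00 × 0.12 = 8.4. Over 10 weeks that is 0.59 to 0.84 dose a week.
- For 5%: 70 × 0.70 × 0.05 = 2.45, up to 70 × 1.00 × 0.05 = 3.5.
- A 12% rise needs baseline adherence of at most 1/1.12 = 89%, and a 5% rise at most 1/1.05 = 95%. Falls of either size are possible from any baseline.

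**3. Chance that such a shift is declared significant** (paired t, N = 128, two-sided 0.05). At the plan's SD of 20: 80% for a 5% shift and over 99.9% for 12%. For 12% at assumed SDs of 33.5 and 50: 98% and 77%.

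**4. What the ratio can show.** If missed doses multiply both levels by k, log(k·6-MMP / k·6-TG) = log(6-MMP/6-TG), so k cancels. The same algebra cancels any timing effect that acts before the pathway divides. Simulated rejection rates (N = 128, paired Wilcoxon, 1,500 runs, assumed SD of log change about 0.2 per metabolite; simulation error about 0.6 points near 5%):

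| Scenario | 6-TG | 6-MMP | log ratio |
|---|---|---|---|
| Adherence −12% | 100% | 100% | 5.0% |
| Adherence +12% | 100% | 100% | 5.6% |
| Upstream timing effect +12% | 100% | 100% | 4.4% |
| Upstream +12% with adherence −10.7% | 6.1% | 5.5% | 4.8% |
| Branch shift: 6-TG +12%, 6-MMP −11% | 100% | 100% | 100% |

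The ratio is protected against adherence and detects a branch shift, but it is blind to an upstream effect. In the fourth row a real upstream effect disappears from all three measures.

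**5. Steady state.** Apply a 12% adherence fall, with each metabolite moving by 12% × (1 − 0.5^(t/half-life)). With assumed half-lives for 6-TG and 6-MMP of 5 and 2, 10 and 5, or 14 and 5 days, a fall held for 70 days changes the ratio by at most 0.42%. A fall confined to the last 7 days changes it by 2.98% to 4.08%. At 30 and 5 days the changes are 2.63% and 5.76%. Cancellation is good for a sustained change and imperfect for a recent one.

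**The case against.** The strongest reply is that the Primary objective concerns assignment to a morning or evening time. If the new time makes patients miss more or fewer doses, that is part of what the assignment does. This stands. It does not cover the enzyme interpretation on which the plan bases the study, nor an adherence change caused by joining the study. The plan's admission that order is uncontrolled discloses that second problem without removing it.

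Second, the data list is not exhaustive: smoking is said to be recorded but is not listed, and the questionnaires and demographics survey are not reproduced. This also stands. The supportable statement is that no adherence measure is described, not that none exists.

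Third, the documents contain no adherence figures, and the two influences on adherence oppose each other. They show that adherence could produce changes of this size, not that it will.

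A reader might infer that the ratio would fully separate adherence from circadian metabolism, and that a circadian effect should be claimed only if the ratio moves. The documents do not support this. The Background places azathioprine conversion and HPRT before the 6-TG/6-MMP division, and the analysis section does not confine the mechanism to the enzymes at that division. Such a rule would reject true upstream effects. Nor is 12% the design target; it is background, and N = 128 rests on 5%.

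**Conclusion.** The concern holds as a limit on interpretation and should be addressed. As described, the plan cannot attribute a change in metabolite levels to enzyme timing, and it remains open to bias from adherence changes that come with enrolment. Fewer than one dose a week could account for a 12% change, and roughly 2.5 to 3.5 doses in 70 for the 5% behind the sample size. These sizes rest on proportionality, one dose a day and an assumed baseline adherence of 70% to 100%.

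This does not invalidate the comparison of assigned times where the time itself alters adherence. The ratio narrows the ambiguity without resolving it, so a record of doses taken and of prescribed dose is needed as well.

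**What to change.** 1. Add the within-patient change in log(6-MMP/6-TG) as a supportive analysis beside the 6-TG and 6-MMP levels. State its reading in advance: a changed ratio supports a shift at the 6-TG/6-MMP division and is not explained by proportional missed doses; an unchanged ratio does not rule out an effect on absorption, azathioprine conversion or HPRT. It should not be a condition for claiming a circadian effect.
2. Add one question on doses missed in the last 4 weeks at baseline and week 10, and record the prescribed dose at both.
3. Report the change in missed doses. Use it as a covariate only in a supportive sensitivity analysis: it arises after assignment, so adjusting for it removes part of the assigned-time effect.

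The ratio needs no new data. The rest costs one question and a dose entry at two existing time points. The downsides are self-report error and a ratio that misses effects moving both metabolites equally, which is why the level analyses stay.

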While circadian based medicine is novel and not yet included in mainstream medical practice, chronotherapy has already shown to be beneficial for treating Rheumatoid Arthritis (RA), another chronic inflammatory disease. In RA, there is temporal variation in cytokine secretion, regulated by the circadian clock, and research has shown that administering drugs at a specific time of day has led to a reduction in symptoms felt by the patient (Buttgerfeit et. al, 2015, p. 4). As explained by Haus et. al, morning stiffness, joint pain, and functional disability in RA is due to differences in the concentration of anti-inflammatory hormone cortisol compared to the concentrations of the pro-inflammatory cytokines that circulate at different times during a 24 hour period (2012, p. 6). Thus, prednisone, a common treatment for RA, if prescribed based on the circadian rhythm levels of IL-6, can control symptoms more effectively (p. 9). Similar to RA and other autoimmune diseases, IBD is characterized by a pro-inflammatory cytokine upregulation with treatments targeting this autoimmune response. Indeed, there is a significant overlap between IBD and RA treatments. Therefore it is possible that time of medication use in IBD may potentially impact the disease outcome. In this regard, we chose to focus on timing of IM delivery because 1) the drug metabolism of IMs is well-characterized (as is explained in detail below) 2) the effective and detrimental metabolites are well known; 3) the levels of these metabolites are clinically monitored in patients on IM therapy; and 4) unlike steroids, where their use should be limited, patients are maintained on IMs for extended time periods.

3. Metabolism of Azathioprine/6-Mercaptopurine

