Our study is based on the potential circadian oscillation of the enzymes responsible for metabolizing IMs (as above), as well as that of the pro- and anti-inflammatory cytokines also described above. The oscillatory nature of these enzymes and cytokines may differ amongst individuals based on their circadian makeup, which we hope to assess via the chronotype surveys (Owl and Lark, MCTQ, RU SATED). We will assess the potential benefit of taking IMs in the morning vs evening by assessing changes in clinical outcomes, laboratory data, endoscopic findings/imaging (if subjects undergo a colonoscopy or imaging as part of their standard care while a part of this study), and quality of life surveys (Harvey Bradshaw, IBDQ). The study is a prospective cross-over study in which each patient is assigned to the morning or evening group based on when they currently take their medication. Therefore, each subject serves as his/her own control.

Study Outcomes: The goal of this study is to determine whether time of delivery of medication affects the efficacy or side effects of this medication. The study outcomes include 1) IBD clinical status as either a) remission defined per no need for step-up therapy (steroid, initiation of anti TNF, change of TNF, or surgery), or b) complications (fistula or abscess) 2) changes in the IBDQ and Harvey Bradshaw questionnaires.

Expected Outcomes: The expected outcome of this study is that there will be a difference seen in disease outcomes for IBD between the different groups based on what time they are taking their medication. Based on the known enzymatic pathways of IM metabolism and their potential circadian rhythm, we expect to see variation in the efficacy as well as toxicity of IMs when administered at different times of the day. Understanding these variations and determining the predicting factors (e.g., chronotypes) can lead to circadian-based administration of IMs to increase the efficacy of the drug while minimizing its side effects. We expect to see differences in the IBD quality of life questionnaire and the Harvey Bradshaw questionnaire from before the intervention to after the intervention, as well as differences in clinical disease activity as determined by levels of metabolites, endoscopic findings, and imaging, between the two groups.

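### Neither blood draw has a clock window and the plan does not specify recording draw or dosing times, which exposes the paired cytokine comparison to draw-time variation and leaves non-switching undetectable

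*Combined protocol and SAP*

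**What the plan says.** All references are to the combined protocol and SAP.

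- **Dosing times (Description of Procedures).** "The group assigned to morning delivery time will be told to take their medication between 6am and 11am" and "The group assigned to evening delivery time will be told to take their medication between 6pm and 11pm". These are the only clock windows in the plan.
- **Baseline draw (same section).** "Lastly, patients will be asked to give a blood sample to test for complete blood count (CBC"; the list continues with the metabolic panel, CRP, 6-MMP and 6-TG. The sentence follows the text on assignment and gives no hour or interval from the last dose.
- **Second draw (same section).** "In addition, a blood sample will be obtained to measure the same metabolite levels and other biochemical indications of disease as stated above". It is placed after 10 weeks, again without an hour.
- **Cytokines (same section).** "Plasma and serum isolated from the blood sample will be temporarily stored to measure inflammatory cytokines after every 20 subjects complete the study". They come from these same untimed draws.
- **Order (Study Design Flow).** The blood draw is listed before the step "Morning or evening group for delivery based on previous time of medication administration", the reverse of the narrative.
- **Recorded data (Data Collection).** The seven listed items include no draw time, dose time or adherence measure. The only time stamps mentioned concern database access.
- **Analysis (Study and Data Analysis).** Cytokines are compared by a paired Wilcoxon test. Covariates are drawn from recorded factors; smoking is the example, and no time variable is named.
- **Premise (same section).** The study rests on potential circadian oscillation of metabolising enzymes and cytokines, and adds that "The oscillatory nature of these enzymes and cytokines may differ amongst individuals based on their circadian makeup".

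**The concern.** If cytokines vary over the day as the study supposes, two samples from one patient taken at different hours will differ even when dosing time has no effect. Variation that is random across patients widens the paired differences and costs power. Variation in a consistent direction between visits shifts the contrast and can imitate or mask an effect. Unrecorded times cannot be adjusted for later.

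Actual dosing times raise a separate issue that touches every endpoint. The intervention consists only of moving the dose. If some patients drift back to their old habit and nobody records it, a null result may mean that timing does not matter or that the switch did not happen.

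The order of the baseline draw matters because a sample taken after the new dosing time has begun is no longer a clean pre-switch value.

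**Working it through.** **1. The plan's own figure.** Inputs from Power and Sample Size: mean difference 5%, SD 20, N = 128, power 80%, alpha 0.05; two-sided from Study and Data Analysis. I take the SD to be in the same percentage units as the difference. Standardised effect d = 5/20 = 0.25. A paired t-test (noncentral t, 127 df) at N = 128 gives power 80.15%. The figure reproduces and serves as the benchmark below. It is not tied to cytokines in particular, and the paired t stands in for the Wilcoxon test.

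**2. Systematic draw-time shift (assumed amplitude).** For a 24-hour cosine of amplitude A, two draws h hours apart differ by at most 2A·sin(πh/24). At h = 4, sin(π/6) = 0.5, so:
- A = 5% of the mean: 2 × 5 × 0.5 = 5%
- A = 10%: 2 × 10 × 0.5 = 10%

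The planned difference is 5%. These are maxima: they need every patient to shift 4 hours in the same direction across the steepest part of the curve.

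**3. Random draw times (assumed).** Both draws are independent and uniform between 8am and 5pm, with A = 10%. The extra SD of the paired difference is √2 times the SD of the cosine over that window. It runs from 2.65 to 8.37 depending on when the peak falls.
- Total SD: √(400 + 2.65²) = 20.17 to √(400 + 8.37²) = 21.68
- Power at N = 128 for a difference of 5: 79% to 74%

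At A = 5% the same calculation gives 80% to 78%. It treats the SD of 20 as free of draw-time variation; if that SD already contains some, the loss is smaller.

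**4. Non-switching (assumed rates).** If a fraction f does not switch and the SD stays at 20, the mean difference becomes 5(1 − f).
- f = 10%: 4.5/20 = 0.225, power 71%
- f = 20%: 4.0/20 = 0.20, power 61%

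**5. Time since dose.** With both draws at 2pm, time since dose is 3-8 h on morning dosing and 15-20 h on evening dosing, so matching the draw hour does not equalise it. Nor should it be a covariate. With doses uniform in the two 5-hour windows and both draws at one hour after the morning window:
- evening-minus-morning difference: mean 12 h, SD √(2 × 25/12) = 2.04 h
- correlation with switch direction, assuming equal numbers each way: 12/√(144 + 4.17) = 0.986
- variance inflation: 1/(1 − 0.986²), which is 148.17/4.17 ≈ 36 before rounding

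The covariate would be almost the intervention itself, and adjusting for it could remove the effect under study.

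**6. Order of the baseline draw.** The narrative puts the draw after assignment and the flow chart before it. No sentence says that it precedes the first dose at the new time.

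**The case against.** Several stronger readings are tempting, and the documents do not support them.

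- **That dosing times are definitely not recorded.** The data list is not exhaustive: smoking is absent from it, yet the analysis section counts smoking among recorded factors. Usual dosing time must be obtained in order to assign patients, and the questionnaires are not reproduced in the text. The supportable statement is that recording is not specified.
- **That the metabolite endpoint is compromised throughout.** Background section 3 says that 6-TG has a long half-life and builds up to steady state, which largely protects it from draw hour and time since dose. No half-life is given for 6-MMP, so that part stays open.
- **That CRP is affected in the same way.** The analysis section names no paired test for CRP, and the documents say nothing about its daily variation.
- **That a cytokine rhythm is established in this disease.** The statement that "there is temporal variation in cytokine secretion, regulated by the circadian clock" describes rheumatoid arthritis. For this study the oscillation is called potential.
- **That a large bias is likely.** Nothing suggests that all draws would move together. Patients switch in both directions, so a common drift partly cancels in a morning-versus-evening contrast unless it follows switch direction. The cancellation depends on balance, which the plan does not fix because assignment follows prior habit.
- **That telephone recruits start early.** This is possible but speculative.

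These objections narrow the point. They do not supply a draw window, a rule for recording times or a consistent order for the baseline sample, and they do not answer the adherence argument.

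**Conclusion.** The point holds as an inexpensive improvement, not as a flaw that invalidates the trial. It is firmest for the paired cytokine comparison, where the study's own premise makes draw hour relevant, and for adherence, where an unrecorded failure to switch would leave a null result on any endpoint uninterpretable. It is weak for 6-TG and undetermined for 6-MMP and CRP.

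The sizes in the working are illustrations. The amplitudes, the 8am-5pm draw range and the non-switching rates are all assumptions, and none has a source in the documents. Within them, the loss from random draw times is modest, while undetected non-switching costs more. The planned N of 128 need not change on this account.

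**What to change.** **In Description of Procedures and Study Design Flow:**
1. Reconcile the two accounts of the baseline draw, and state that the baseline sample is taken before the first dose at the new time.
2. Take both samples of a patient in the same clock window, for example within 1 hour of each other.
3. At both visits, record draw clock time, time of last dose and actual dosing times over the preceding week. Add these to the Data Collection list.

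**In Study and Data Analysis:**
1. Add a sensitivity analysis of patients who dosed in their assigned window, labelled supportive because it selects on adherence.
2. Add a sensitivity analysis adjusting the cytokine comparison for the between-visit difference in draw clock time.
3. Report time since dose descriptively, and do not adjust for it.

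**Cost:** protocol wording, three extra form fields and slightly less flexible appointments. No visits or samples are added, and the prescribed treatment is untouched.

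### The primary endpoint is "metabolites" in the plural: two are measured, and the plan does not say which is primary, whether one or both must differ, or how multiplicity is handled

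*Combined protocol and SAP*

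**What the plan says.** Study and Data Analysis gives the primary endpoint in one sentence: "The primary endpoint of this study will be metabolites of 6-mercaptopurine". The same paragraph sets the error rate: "we assume a Type I error rate of 0.05 and a 2-sided test for all analyses". It describes one comparison, "with a paired Wilcox Signed Rank test at alpha=0.05 level", without naming the analyte.

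Description of Procedures lists two metabolites in the baseline blood sample: "methylmercaptopurine (6-MMP), and thioguanine nucleotides (6-TG". After 10 weeks "a blood sample will be obtained to measure the same metabolite levels". The Background section on metabolism of the two drugs links 6-TG to immunosuppression and, at high levels, to marrow suppression. It links 6-MMP to hepatotoxicity.

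There are two power statements for the same 128 subjects:
- Power and Sample Size, at 80% power: "For a mean difference of 5% and standard deviation of 20, we calculated that we will need to enroll 128 subjects". It names no endpoint.
- Study and Data Analysis: "With 128 UC subjects and effect size of 0.1 this will give us a 98% power to detect a difference in serum metabolites". It says which family of measurements is meant, but not which member.

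The numbered list under Study Outcomes gives clinical status and changes in two questionnaires. It does not list metabolites.

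**The concern.** 6-TG and 6-MMP are not two readings of one quantity. On the plan's own account one relates mainly to effect and the other to toxicity, and they may move differently when dosing time changes. A result on 6-TG alone, on 6-MMP alone, or on both would support different conclusions. The plan would allow any of these to be reported as the primary result, because it has no rule for success.

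The missing rule affects either the error rate or the power. If a difference in either metabolite is enough, two tests at 0.05 give more than a 5% chance of a false primary claim. If both must differ, the error rate is protected, but the power is that of a joint requirement, which neither power statement addresses.

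**Working it through.** **Inputs from the plan.** Two metabolites; two-sided alpha 0.05; 128 subjects; mean difference 5 and SD 20; effect size 0.1 with 98% power; paired Wilcoxon signed rank test.

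**Assumptions not in the plan.** Correlation between the two test statistics of 0, 0.5 or 0.7; normally distributed within-patient differences; the standardised effect of 5/20 = 0.25 applied to each metabolite; 128 complete pairs.

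**1. The plan's sample size.** With d = 5/20 = 0.25, the normal approximation for a paired comparison is n = ((1.960 + 0.842)/0.25)² = 125.6, so 126. The exact paired t calculation gives n = 128, with power 80.2%. The figure of 128 therefore reproduces for one paired t test on one variable.

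**2. The same 128 under the planned test.** For normal differences the Wilcoxon signed rank test has efficiency 3/π = 0.955 relative to the t test. Then 128 × 0.955 = 122 effective pairs, and power is 78% (simulation also gives 78%). Reaching 80% takes about 128/0.955 = 134 pairs.

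**3. Either metabolite suffices.** With independent tests the chance of at least one false positive is 1 − (1 − 0.05)² = 0.0975. With correlated tests it is 1 − P(|Z₁| < 1.96 and |Z₂| < 1.96) under a bivariate normal distribution.

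**4. Both must differ.** The false-positive rate is at most 0.05. With independent tests joint power is the product of the single powers, about 0.78 × 0.78 = 0.61 (0.616 by simulation). Correlation raises it.

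| Correlation (assumed) | False-positive rate, either suffices | Wilcoxon power, both required, 128 pairs | Pairs for 80%, both required |
|---|---|---|---|
| 0 | 9.75% | 62% | about 175 |
| 0.5 | 9.1% | 66% | about 166 |
| 0.7 | 8.3% | 69% | about 160 |

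Simulated Wilcoxon tests with 128 pairs gave false-positive rates of 9.5%, 9.2% and 8.3%, in line with the second column.

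**5. The 98% figure.** If 0.1 is a standardised paired difference, power with 128 pairs is 20% by paired t and 19–20% by Wilcoxon. A paired t power of 98% needs d of about 0.36. So this statement cannot stand in for a rule on the two metabolites.

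**6. Direction of the difference.** Of the two switch directions, one is stated as "Patients who currently take their medication in the morning will be asked to switch to an evening delivery", and evening takers switch the other way. If evening dosing raises a level by δ, the week-10-minus-baseline change is +δ in the first group and −δ in the second. Pooled, these offset each other. Taken as evening minus morning, both are +δ.

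**The case against.** Several points on the other side have force.

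- **Timing of the choice.** A reader might infer that the sponsor will pick the metabolite after seeing the results. The documents do not say when the choice is made. They permit a late choice and do not require one.
- **Meaning of 0.05.** The level set for all analyses can be read as a per-test level. The 8–10% is then an excess over a family-wise standard that the plan never states, and it arises only if either metabolite suffices. This stands as a qualification. But the plan declares a primary endpoint and claims power for it, so a reader will take 5% as the error rate of the primary claim.
- **Power.** A reader might infer that requiring both metabolites simply breaks the plan's 80%. The documents do not support that without a condition, because the 80% is attached to no endpoint. The only figure attached to metabolites is 98%, and two independent tests at 98% would give 0.98² = 96% joint power. The lower figures here depend on carrying the 0.25 over to each metabolite. Against this, the 98% is not reproduced if 0.1 is a standardised difference.
- **Outcome list.** The Study Outcomes list is introduced as inclusive, not exhaustive. Nearby text mentions laboratory data and metabolite levels, and the primary endpoint is stated outright elsewhere. Its absence from the list is a drafting inconsistency, not a contradiction.
- **Clinical status.** A reader might infer that this outcome leaves some subjects unclassifiable. That holds only if (a) remission and (b) complications are categories of one variable. A subject with step-up therapy and no fistula or abscess would then fit neither. Read as two yes/no outcomes, they classify everyone.
- **Remission.** The word serves both a Harvey Bradshaw score band and a definition based on need for step-up therapy. These are two measures, and no conflict is shown.

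None of this supplies a primary metabolite, a success rule or a multiplicity rule.

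**Conclusion.** The point holds for the primary endpoint. Two distinct metabolites share the primary position at two-sided 0.05 each, with no rule connecting them.

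If either counts, the false-positive rate for the primary claim is 9.75%, 9.1% or 8.3% at assumed correlations 0, 0.5 and 0.7. The exact size depends on a correlation that the documents do not give, but the rate exceeds 5% unless the two tests are perfectly dependent. If both must differ, the error rate holds. Joint Wilcoxon power is then about 62–69% against about 78% for one named metabolite, assuming a standardised effect of 0.25 on each, normal differences and 128 complete pairs.

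The clinical-status wording and the outcome list are minor, and the first is conditional on how the text is read. This should be corrected before data are examined. It does not invalidate the design.

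**What to change.** Before data are examined:

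1. Name one primary metabolite. 6-TG or 6-MMP is the sponsor's choice; the plan gives a rationale for interest in each.
2. Define its measure as the within-patient difference, evening minus morning: week 10 minus baseline for those switched to evening, baseline minus week 10 for those switched to morning.
3. Test it with the planned Wilcoxon signed rank test at two-sided 0.05. Test the other metabolite at 0.05 only if the first is significant. In simulation with no true difference in either metabolite, this sequence gave a false-positive rate of 4.9–5.1% for correlations from −0.7 to 0.7.
4. Label all other outcomes secondary, and add the primary endpoint to the Study Outcomes list.
5. Restate power for the named metabolite, the Wilcoxon test and the expected number of complete pairs, without claiming 98%, or 80% from 128 enrolled.
6. State that remission and complications are two separate yes/no outcomes, if that is what is meant.

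**Cost.** The endpoint rule is a matter of wording and needs no new data. The second metabolite alone can no longer make the trial positive. At an effect of 0.25 on each, the chance that both are significant is still only about 62–69%. The stated power becomes less favourable: about 78% if all 128 form complete pairs, and about 73% with 115 pairs (128 × 0.9 = 115.2; the 10% loss is an assumption, since the plan gives no rate).
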